3.8 Efficacy Analyses

All efficacy analyses will be based on the FAS. Additionally, the analysis of the primary endpoint will be repeated on the PPS to assess the sensitivity of the results to major protocol violations. All efficacy variables will be summarized descriptively by treatment group and visit, including observed, change from baseline, and percent change from baseline, if appropriate. Sensitivity analyses to assess the impact of

missing primary endpoint data will be conducted on the FAS analysis set and are described below.

3.8.1 Primary Efficacy Endpoint Analyses

The CGI-I-AS scale assessed by the clinician will be collected at Week 6 and 12 visits. This is an ordinal variable with scores ranging from 1 (very much improved), 4 (no change), to 7 (very much worse) which will be analyzed as a continuous/ordinal outcome variable in these analyses. The normality of CGI-I-AS at Week 6 and Week 12 for each treatment group will be examined. The examination of CGI-I-AS at each visit to ascertain the degree of departure from normality will involve generating bar charts, histograms, box-plots and normal probability plots, to visually evaluate the skewness and the kurtosis of the CGI-I-AS Week 6 and Week 12 data.

Descriptive statistics will be displayed for CGI-I-AS total improvement score at each visit by treatment group for the FAS. Frequencies and percentages will also be tabulated for the number of subjects with each specific score, the number of subjects with a response of at least minimally improved, and the number of subjects with a response of at least much improved by treatment group and overall. A response of at least minimally improved is defined as a CGI-I-AS score of 1, 2, or 3. A response of at least much improved is defined as a CGI-I-AS score of 1 or 2.

A separate summary will also be displayed for CGI-I-AS total improvement score at each visit for each age group at randomization (4 to 8 years or 9 to 12 years) within treatment group and all age groups combined within treatment group. The 95% CIs will be calculated for the mean difference in the CGI-I-AS total improvement score by week and age group for OV101 versus placebo. Frequencies and percentages will also be tabulated for the number of subjects with each specific score, the number of subjects with a response of at least minimally improved, and the number of subjects with a response of at least much improved by age group within treatment group and all age groups combined within treatment group.

Descriptive statistics will also be displayed for CGI-I-AS total improvement score at each visit by treatment group, separately for each stratification region (US, outside US). An additional table displaying CGI-I-AS total improvement score at each visit by treatment group, separately for each country will also be presented.

In addition, a separate summary will also be displayed for CGI-I-AS total improvement score at each visit for each method of CGI-I-AS assessment. For this analysis, subjects will be grouped into the remote/phone visit collection group if any CGI-I-AS assessment is conducted remotely and into the on-site visit collection group if none of the CGI-I-AS assessments are conducted remotely.

As the primary analysis, a Mixed Model Repeated Measures (MMRM) Analysis of Variance (ANOVA) model will be fitted using restricted maximum likelihood (REML) for CGI-I-AS with fixed effects for visit (Weeks 6 and 12), randomized treatment, the visit-by-treatment interaction, age group (randomization stratification variable: age 4 to 8 years versus age 9 to 12 years), and region (randomization stratification variable: US versus outside US) for the FAS. An unstructured within subject-covariance structure is preferred and will be specified first. If the model converges, the Kenward-Roger approximation will be used to estimate the denominator degrees of freedom.

If the model with unstructured covariance fails to converge, the following covariance structures will be tested in this order: toeplitz with heterogeneity, autoregressive with heterogeneity by visit, compound symmetry with heterogeneous variances by visit, toeplitz, autoregressive, and compound symmetry without heterogeneous variances by visit. The first covariance structure that converges will be used for the analysis. If a structured covariance is used, then a robust sandwich estimator will be utilized for estimating the variance of the treatment effect estimate.

From the model, the Week 12 difference between least squares means of OV101 and placebo groups will be presented along with the corresponding 95% confidence interval and 2-sided *P*-value. This analysis will be repeated for the PPS. Furthermore, as an additional supportive analysis, this analysis will also be repeated based on method of CGI-I-AS assessment collection (remote/phone or on-site) as described above.

As supportive analysis, an ANOVA on the Week 12 data will be performed (observed case analysis) for the FAS and PPS with effects for randomized treatment, age group, and region.

As sensitivity analysis of the normality assumption for Week 12 CGI-I-AS data, a Wilcoxon rank sum exact test, with a continuity correction of 0.5, will be used for treatment group comparison of Week 12 CGI-I-AS scores for the FAS and PPS. The 2-sided exact *p*-value will be presented. The Hodges–Lehmann estimate of the median CGI-I-AS difference between OV101 and placebo groups, and its 95% confidence interval will also be presented.

If more than 3% of CGI-I-AS values at Week 12 are missing, a sensitivity analysis involving multiple imputation will be conducted. Additionally, if more than 5% of CGI-I-AS values at Week 12 are missing, a tipping point analysis will be also performed. Details are specified in the Section 3.8.6.

In addition to the supportive analyses mentioned above, an additional supportive analysis will be conducted in which CGI-I-AS assessments from unscheduled visits and end of treatment (EOT) visits from subjects discontinuing treatment early (before

Week 12) will be mapped using alternative visit window mapping (see Table 3 section 3.1.8).

For this analysis, descriptive statistics will be displayed for CGI-I-AS total improvement score at each visit by treatment group for the FAS. Frequencies and percentages will also be tabulated for the number of subjects with each specific score, the number of subjects with a response of at least minimally improved, and the number of subjects with a response of at least much improved by treatment group and overall.

An MMRM ANOVA methodology similar to the one described above will also be performed after mapping the CGI-I-AS assessments using the alternative visit mapping (Table 3). From the model, the Week 12 difference between least squares means of OV101 and placebo groups will be presented along with the corresponding 95% confidence interval and 2-sided *P*-value.

An additional supportive analysis will be conducted in which CGI-I-AS assessments will be analyzed according to the nominal visit time point as defined in section 3.1.8. Descriptive statistics will be displayed for CGI-I-AS total improvement score at each visit by treatment group for the FAS. An MMRM ANOVA analysis as described above will also be presented.

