7.8.1 Primary Efficacy Analyses

The CGI-I-AS scale assessed by the clinician rater will be collected at the Week 6 and Week 12 visits. This is an ordinal variable with scores ranging from 1 (very much improved), to 4 (no change), to 7 (very much worse) which will be analyzed as a continuous outcome variable in these analyses.

An MMRM Analysis of Variance (ANOVA) model will be fitted using restricted maximum likelihood (REML) for CGI-I-AS with fixed effects for visit (Week 6 and Week 12), randomized treatment, the visit-by-treatment interaction, age group (randomization stratification variable: age 4 to 8 years versus age 9 to 12 years), and region (randomization stratification variable: US versus outside US). An unstructured within -subject covariance structure will be specified as the first choice, and if the model fails to converge, alternative covariance structures will be tested as detailed in the SAP. If a structured covariance is used, then a robust sandwich estimator will be utilized for estimating the variance of the treatment effect estimate. From the model, the Week 12 difference between least squared means of OV101 and placebo groups will be presented along with the corresponding 95% confidence interval and 2-sided *P* value.

[figure not shown]
As a sensitivity analysis for the assumption of normality, a Wilcoxon rank sum test will be used for treatment group comparison. The Hodges–Lehmann (Hodges and Lehmann 1963) estimate of

the median CGI-I-AS difference between OV101 and placebo groups, and its 95% confidence interval will be presented along with the 2-sided *P* value.

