2.2.3 Efficacy Assessments

Efficacy assessments will include the CGI-I-AS and CGI-S-AS scales, [REDACTED]

[REDACTED]

CGI-S-AS will be collected at Screening, Baseline, Weeks 6 and 12. CGI-I-AS will be assessed at Weeks 6 and 12. [REDACTED] will be obtained at Baseline, Week 6 and Week 12. The VABS-3 and [REDACTED] instruments will be administered at Baseline and Week 12.

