2.2.3.1 Clinical Global Impressions Scales

The CGI-S-AS scale with AS-specific anchors will be used by the investigator to assess the severity of symptoms, and the CGI-I-AS scale will be used by investigators to assess improvement from baseline. The CGI-S-AS has been adapted to capture specific characteristics commonly present in the AS population. The CGI-I-AS captures clinical impression that reflects the rater's estimate of change from the initiation (Baseline) of treatment. Both the CGI-S-AS and the CGI-I-AS assessments will be conducted by a clinician rater with experience in AS and trained in CGI-S-AS and CGI-I-AS rating by the Sponsor. The rater should be the same rater throughout the study for a given subject (on the eCRF, the investigator will be identified as either the same or different since the last time the subject was seen). As an exception, a clinician sub-investigator, trained in CGI-S-AS and CGI-I-AS rating by the Sponsor, may be used. The Baseline CGI-S-AS will be accompanied by detailed Investigator Notes. Each CGI-I-AS rating at Week 6 and Week 12 will also be accompanied by detailed Investigator Notes. In order to reduce recall bias, within 24 hours prior to the Week 6 CGI-I-AS rating, the rater will review the CGI-S-AS rating and Investigator Notes from the baseline visit and within 24 hours prior to the Week 12 CGI-I-AS rating, the rater will review the CGI-S-AS rating and Investigator Notes from the baseline visit and CGI-I-AS rating and Investigator Notes from Week 6. If the CGI-I-AS assessment is missing at Week 6 or 12, the reason for its absence will be collected on the eCRF.

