3.1.4 Baseline Value and Change from Baseline

Baseline value is defined as the latest non-missing value obtained prior to administration of first dose, [REDACTED]

[REDACTED] Change from baseline will be calculated by subtracting the baseline value from the post-dose assessment for each subject (i.e., post-dose – baseline).

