If more than 3% of CGI-I-AS values at Week 12 are missing, as a sensitivity analysis, missing data will be imputed using the multiple imputation (MI) procedure. The imputation strategy described in Ouyang (2017) will be implemented for this study. There are only two visits where CGI-I-AS is assessed, hence, there are 2 possible missing patterns in the CGI-I-AS data: 1) Week 6 assessment is missing and Week 12 assessment is present (non-monotone pattern); or 2) Week 12 assessment is missing but Week 6 assessment is present (monotone pattern). In general, the MAR assumption is reasonable for intermittent missing values before a subject is discontinued because the data before and after the intermittent missing value are known. In this case, if Week 6 CGI-I-AS is missing but Week 12 CGI-I-AS is assessed (missing data pattern 1), it is reasonable to consider the missing Week 6 data as MAR. However, missing CGI-I-AS at Week 12 after the subject is withdrawn from the trial may or may not be MAR. Multiple imputation will first be implemented under the MAR assumption. To assess the appropriateness of the MAR assumption, additional sensitivity analyses using a tipping point approach will be performed under scenarios assuming missing not at random (MNAR) for the missing data pattern 2 above.

Multiple Imputation Procedure under MAR assumption will be conducted as follows using SAS PROC MI:

1. Missing Week 6 CGI-I-AS data points will be imputed under MAR assumption using a logistic regression model for ordinal data with randomized treatment, age group, region, and CGI-S-AS Overall Score at Baseline as independent variables.
2. Missing Week 12 CGI-I-AS data points will be imputed under MAR assumption using a logistic regression model for ordinal data with randomized treatment, age group, region, CGI-S-AS Overall Score at Baseline, and the Week 6 CGI-I-AS as independent variables.
3. Thirty complete imputed datasets will be generated by repeating the above steps 30 times.
4. The primary MMRM analysis of CGI-I-AS described above will be performed for each of the 30 complete imputed data sets.

5. The estimated treatment effects will be combined across the 30 analyses using SAS PROC MIANALYZE.

If the treatment effect is significant in the analysis using the MI procedure under MAR, with significance level of 0.05 and more than 5% of CGI-I-AS values at Week 12 are missing, a tipping point analysis will be conducted.

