5 PROGRAMMING SPECIFICATIONS

5.1 Analysis Specifications

Sample SAS code for the MMRM ANCOVA analysis is as follows:

```
proc mixed data=temp method=reml;
  class subject visit treat agegrp region;
  model endpoint = visit treat agegrp region baseline
  visit*treat ;
  repeated visit / subject=subject type=covstruc;
  lsmeans visit*treat / diff=all cl alpha=0.05;
run;
```

Use the following sequence for choosing a covariance structure, covstruc.

Use the first covariance structure that converges:

SAS Name for Covariance Structure	Covariance Description
UN	Unstructured
TOEPH	Heterogeneous Toeplitz
ARH(1)	Heterogeneous Autoregressive(1)
CSH	Heterogeneous Compound Symmetry
TOEP	Toeplitz
AR(1)	Autoregressive(1)
CS	Compound Symmetry

If the model converges with an unstructured covariance matrix, the Kenward-Roger approximation will be used to estimate the denominator degrees of freedom. If a structured covariance is used for the model, then a robust sandwich estimator will be utilized for estimating the variance of the treatment effect estimate.

For the MMRM ANOVA model, baseline is excluded from the model statement.

Sample SAS code for the generalized logit model analysis is as follows:

```
PROC GLIMMIX DATA = xxx;
  CLASS subject visit treat agegrp region;
  MODEL endpoint = visit treat agegrp region visit*treat /
  DIST= b link=logit;
  random intercept / subject=subject type = covstruc;
  LSMEANS visit*treat / diff exp cl or;
RUN;
```

Use the sequence for choosing a covariance structure, covstruc, described above with the unstructured covariance replaced by an unstructured Cholesky covariance.

Sample SAS code for the logistic analysis is as follows:

```
PROC LOGISTIC DATA = xxx;  
  CLASS treat agegrp region;  
  MODEL endpoint = treat agegrp region;  
  LSMEANS treat / diff cl or;  
RUN;
```

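### The primary MMRM leaves out baseline CGI-S-AS Overall, a pre-dose score already held for essentially every child; adding it risks about 0.6 power points and could gain several

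*SAP*

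**What the plan says.** SAP 3.8.1 specifies the primary model "for CGI-I-AS with fixed effects for visit (Weeks 6 and 12), randomized treatment, the visit-by-treatment interaction, age group" and region. Protocol 7.8.1 has the same terms: "the visit-by-treatment interaction, age group (randomization stratification variable: age 4 to 8 years versus age 9 to 12 years), and region". The programming section, SAP 5.1, confirms the form: "For the MMRM ANOVA model, baseline is excluded from the model statement".

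The other linear models for this endpoint are also without a severity term. The supportive Week 12 ANOVA in SAP 3.8.1 has treatment, age group and region. For the alternative visit windows, "An MMRM ANOVA methodology similar to the one described above will also be performed after mapping the CGI-I-AS assessments", and the nominal-visit analysis also repeats the primary method. The MMRM run on multiply imputed data (SAP 3.8.6) is the primary model again.

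The plan collects and uses baseline severity elsewhere:

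- SAP 2.2.3: "CGI-S-AS will be collected at Screening, Baseline, Weeks 6 and 12".
- SAP 3.1.4: "Baseline value is defined as the latest non-missing value obtained prior to administration of first dose".
- Protocol 4.1.1 requires a CGI-S-AS score of at least 3 for entry.
- SAP 2.2.3.1: before each CGI-I-AS rating "the rater will review the CGI-S-AS rating and Investigator Notes from the baseline visit".
- SAP 3.8.6: the Week 12 imputation step includes "CGI-S-AS Overall Score at Baseline, and the Week 6 CGI-I-AS as independent variables". The Week 6 step also uses the baseline score.
- SAP 3.8.3: MMRMs for change from baseline adjust for the endpoint's own baseline, and so do the VABS-3 ANCOVAs. The relation of baseline CGI-S-AS to Week 12 CGI-I-AS is to be explored by Pearson correlation within each arm.

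**The concern.** A pre-dose score that explains part of the variation in Week 12 CGI-I-AS would narrow the confidence interval if it were in the model. This score should be present for essentially every randomized child, so including it should drop nobody. No reason for leaving it out appears in the text available.

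At stake is precision on the only test that opens the fixed sequence, in a trial planned around 80 completers. A chance imbalance in baseline severity would also go unadjusted, and an adjustment chosen after unblinding would be open to dispute.

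Missing data add a secondary reason. The plan allows for about 1 − 80/90 = 11% loss. The primary MMRM assumes data missing at random given its own terms, whereas the imputation analysis assumes it given those terms plus baseline CGI-S-AS. Adding the score would align the two.

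**Working it through.** There is no planned power figure to reproduce: Protocol 7.3, which SAP 2.2.1 cites for the sample size, is not in the text available.

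**Inputs**

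- Completers: N = 80, 40 per arm (Protocol 4.1 and 4.2.3). Randomized: about 90 (SAP 2.2.1).
- Test: two-sided, alpha 0.05 (SAP 3.1.3).
- Effect: d = 0.634 SD, assumed. It gives 80% power in a plain two-sample t-test at 40 per arm.
- r: partial correlation of baseline CGI-S-AS Overall with Week 12 CGI-I-AS after age group and region. The documents give no value; assumed range 0 to 0.5.

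**Method.** A Week 12 linear model approximates the MMRM. Power comes from the noncentral t distribution with noncentrality d × √(20 / V), where V is the variance factor.

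- Current model (age group, region): df = 76, V = 1 + 2/75 = 1.0267. Noncentrality = 0.634 × √(20/1.0267) = 2.80, and power = 78.9%.
- Adjusted model (one more covariate): df = 75, V = (1 + 3/74) × (1 − r²).
- Variance ratio, adjusted to current: (1 − r²) × (1 + 1/74). Equivalent number of children = 80 / ratio. The change in CI width also carries the slightly larger t quantile at 75 df.

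| r | Power, adjusted | Variance ratio | Change in CI width | Equivalent children |
|---|---|---|---|---|
| 0 | 78.4% | 1.014 | +0.7% | 79 |
| 0.1 | 78.8% | 1.003 | +0.2% | 80 |
| 0.2 | 80.0% | 0.973 | −1.3% | 82 |
| 0.3 | 82.1% | 0.922 | −3.9% | 87 |
| 0.4 | 85.0% | 0.851 | −7.7% | 94 |
| 0.5 | 88.7% | 0.760 | −12.8% | 105 |

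The loss at r = 0 is about 0.55 points before rounding.

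**Break-even.** Setting (1 − r²)(1 + 1/74) = 1 gives r² = 1/75, so |r| = 0.115. Solving on power instead gives |r| = 0.117. With 90 completers the variance break-even is 0.109.

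**Dependence on the assumed base power.** With the current model anchored at exactly 80%, 85% or 90% power and N = 80, the loss at r = 0 is 0.53, 0.48 or 0.39 points. It peaks at about 0.58 points when base power is near 65 to 70%. The gain at r = 0.3 is 3.1 points from 80% and 2.1 from 90%.

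**Checks by simulation**

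- Week 12 linear model, N = 80, 20,000 trials per setting: power fell by 0.55 points at r = 0. Variance ratios were 1.011 at r = 0, 0.999 at r = 0.12 and 0.928 at r = 0.3.
- Two-visit REML MMRM, unstructured covariance, 45 per arm, about 10 of 90 Week 12 values missing at random, assumed between-visit correlation 0.6, 800 runs per r: the Week 12 standard error, adjusted to current, was 1.004, 1.000, 0.985, 0.961, 0.925 and 0.880 for r from 0 to 0.5 in steps of 0.1. Adding a covariate-by-visit term raised each ratio by about 0.002. Mean treatment estimates agreed within 0.006.

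**The case against.** The model as written is valid. It is prespecified, consistent between the two documents, and adjusts for both stratification factors, so a further covariate is an efficiency choice and not the repair of an error. That stands.

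The benefit depends on an unknown r, and there are reasons to expect it to be small. CGI-I-AS is itself a rating of change made after reviewing baseline severity, and the entry criterion narrows the range of the score. At r = 0.2 the gain is only about 1.1 points, and nothing in the documents makes 0.3 or more likely. That also stands, and it limits the weight of the point. It does not reverse the trade-off, because the loss if r is zero is about half a point.

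Some of the supporting evidence proves little about prognostic value:

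- The SAP 5.1 sentence concerns the endpoint's own baseline, which CGI-I-AS lacks, and records no decision about CGI-S-AS.
- The imputation is a sensitivity analysis run only if more than 3% of Week 12 values are missing, and imputation models may properly hold extra predictors.
- Adjusting a computed change score for its own baseline is a different case.

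These are fair. Those passages show only the form of the model and that the covariate is on hand.

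Finally, a supportive adjusted model would add no power to the primary test. That is correct; only a change to the primary model does so.

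**Conclusion.** The point holds as a missed opportunity for precision. The current analysis is neither biased nor anticonservative with complete data. With 80 completers, adjusting for baseline CGI-S-AS Overall costs about 0.6 power points at most if the score is unrelated to outcome. It breaks even at |r| of about 0.12 and gains about 3 points at r = 0.3 and nearly 10 at r = 0.5. At r = 0.3 it is worth about 7 extra children, which matters in a rare disease.

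The size rests on two assumptions: a base power of about 79%, and a range of 0 to 0.5 for r. Below about r = 0.3 the gain is too small to matter. The change should be made because its downside is small and bounded, but it is not critical to the validity of the trial.

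**What to change.** Before unblinding, add baseline CGI-S-AS Symptoms Overall as a covariate in the primary MMRM, optionally with its visit interaction. Carry it into the PPS repeat, the Week 12 ANOVA and the MMRM on imputed data. The alternative-window and nominal-visit MMRMs repeat the primary method and would follow. Keep the present model as a supportive analysis. State that the covariate is fixed, so that the VABS-3 rule of dropping baseline after an interaction test is not read across. Whether the responder models take the same covariate is a separate decision to record.

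If the sponsor keeps the primary model as it is, the adjusted model should be prespecified as supportive and the reason given, on the understanding that this adds no power to the primary test.

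The cost is one term in SAP 3.8.1 and 5.1 and Protocol 7.8.1, one degree of freedom (two with the visit interaction), and no new data. Under Protocol 7.1 an amendment is needed if the change is judged substantial; otherwise the SAP must describe and justify it.

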2.2.2 Randomization and Blinding Procedures

Eligible subjects are required to sign the informed consent form (ICF), complete the screening period and assessments, and meet all inclusion/exclusion requirements.

Eligible subjects 4 to 12 years old (inclusive) will be assigned in a 1:1 ratio on Day 1 to receive investigational product according to a computer-generated randomization schedule. Subjects will be assigned to treatment groups in sequential order as they qualify for the study, using a centrally located and managed IWRS. Randomization will be stratified by age categories: 9 to 12 years old (inclusive) and 4 to 8 years old (inclusive), and region: US and outside US, with at least 24 subjects per age category. Upon randomization, each subject will receive a subject randomization number and a drug kit assignment.

This is a double-blind, placebo-controlled study. The sponsor, investigators, study coordinators, pharmacists, and study subjects will be blinded to the study medication. To maintain blinding of the individual treatment assignment, the results of [REDACTED] will not be made available to any study personnel or subjects.

If knowledge of the treatment is needed to manage the subject's condition, the investigator will contact the IWRS to obtain the treatment assignment. If unblinding occurs for any reason, the time and reason for breaking the blind will be recorded on the electronic case report form (eCRF) and the sponsor must be notified within 24 hours.

A designated statistician who is not involved with the study operation will hold the treatment codes. The Independent Data Monitoring Committee (IDMC) will review blinded data, but will also have the ability to review unblinded data as needed to evaluate benefit risk during the study. For example, the unblinded treatment information can be provided to the IDMC to facilitate the evaluation of any clinically important increase in the rate of a serious suspected adverse reaction or to the designated safety contact when the treatment information is required to determine if an expedited safety report must be submitted to regulatory agencies. The IDMC and relevant unblinded personnel should prevent any risk of unblinding of data to the sponsor, investigators, study coordinators, pharmacists, and study subjects.

Eligible subjects 2 to 3 years old (inclusive) will be treated with OV101, and their treatment is not blinded.

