The tipping point analysis will focus on the imputed CGI-I-AS values which may be MNAR (missing data pattern 2 above). These analyses will start with the 30 imputed datasets created under a MAR assumption as described above. For each dataset, the imputed values of CGI-I-AS for the OV101 group (with missing pattern 2) will be worsened by adding 1 (unless the current value is the highest level on the CGI-I-AS scale [7=very much worse]). The placebo group imputed values will remain unchanged. After the OV101 group's imputed Week 12 CGI-I-AS data have been "worsened" by 1 point for those with missing pattern 2, the MMRM model used in the primary analysis will be fitted to the data and the estimated treatment effects will be combined using SAS PROC MIANALYZE. This process will be repeated, at each step incrementally worsening by 1 the imputed values of CGI-I-AS for the OV101 group, until the treatment effect is no longer significant (p-value for the treatment comparison ≥ 0.05).

As a sensitivity analysis, the following rank-based imputation strategy described in Ouyang (2017) will also be implemented when more than 5% of CGI-I-AS values at Week 12 are missing. This analysis will include both subjects with a Week 12 CGI-I-AS and subjects who discontinued prior to the Week 12 assessment, without the need for multiple imputation methodology and the associated assumptions. This approach assumes that discontinuation from the trial is detrimental so it penalizes the treatment group with more early discontinuations. The subjects will be first divided into 2 sets according to their CGI-I-AS assessments: 1) those with a Week 12 CGI-I-AS; and 2) those with a Week 6 CGI-I-AS but no Week 12 CGI-I-AS. Within the two sets, subjects will be ranked separately (based on the Week 12 CGI-I-AS for set 1 and the Week 6 CGI-I-AS for set 2). The lowest rank will be given to the largest CGI-I-AS within that set. The Wilcoxon Rank-Sum test will then be applied to this ranking instead of ranking solely based on the Week 12 CGI-I-AS for completers.

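### The Wilcoxon sensitivity tests of Week 12 CGI-I-AS leave out the age and region strata used for randomisation; if those strata are prognostic, the tests are conservative and lose power

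*SAP*

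**What the plan says.** **Allocation.** SAP 2.2.2: "Randomization will be stratified by age categories: 9 to 12 years old (inclusive) and 4 to 8 years old (inclusive), and region: US and outside" the US. That makes four cells. At least 24 children are required in each age group; no minimum is set for either region.

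**Adjusted analyses.** The primary MMRM in SAP 3.8.1 has fixed effects that include "age group (randomization stratification variable: age 4 to 8 years versus age 9 to 12 years), and region (randomization stratification variable: US versus outside US)". The observed-case Week 12 ANOVA in the same section, the responder models in SAP 3.8.2 and the multiple-imputation models in SAP 3.8.6 also carry both factors.

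**Rank tests.** SAP 3.8.1 introduces the Wilcoxon test with the words "As sensitivity analysis of the normality assumption for Week 12 CGI-I-AS data" and continues: "a Wilcoxon rank sum exact test, with a continuity correction of 0.5, will be used for treatment group comparison of Week 12 CGI-I-AS scores". It is applied to the FAS and PPS, with an exact two-sided p-value and a Hodges–Lehmann estimate, and no strata are named. Protocol 7.8.1 has the same test: "As a sensitivity analysis for the assumption of normality, a Wilcoxon rank sum test will be used for treatment group comparison". SAP 3.8.6 adds a second rank test, which runs only if more than 5% of Week 12 values are missing. Completers and dropouts are ranked as two sets, and then: "The Wilcoxon Rank-Sum test will then be applied to this ranking instead of ranking solely based on the Week 12 CGI-I-AS for completers". Again no strata are named.

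**Status.** Under SAP 3.1.3 only the MMRM and the two responder tests carry alpha. Both Wilcoxon tests are sensitivity analyses.

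**The concern.** When allocation is balanced within strata, differences between strata add almost nothing to the true variability of the treatment comparison. A pooled rank test still counts them in its variance. If the strata predict outcome, the test statistic is therefore too small, the true size falls below 5% and power is lost.

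The stake is how a disagreement would be read. The test exists to show whether the result depends on normality, and its closest comparator is the observed-case Week 12 ANOVA, which uses the same visit and the same analysis sets. Moving from that ANOVA to the pooled Wilcoxon changes two things at once: the normality assumption and the adjustment for strata. A non-significant Wilcoxon beside a significant adjusted analysis could then be put down to non-normality when the cause is the missing stratification.

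**Working it through.** The documents state no size or power for the rank tests, so there is no figure to reproduce. The effect was simulated.

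**Inputs from the documents**
- About 90 randomised 1:1 (SAP 2.2.1); at least 80 evaluable (Protocol 4.2.3).
- Four age-by-region cells (SAP 2.2.2).
- Two-sided 0.05, the level of the primary test (SAP 3.1.3).
- Placebo distribution from the Phase 2 study in Protocol Section 1: 7.4% much improved, 14.8% minimally improved.

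**Assumptions (not in the documents)**
- The remaining placebo children are split 70.0% at score 4 and 7.8% at score 5.
- Permuted blocks of 4 within cells.
- Age split 50/50, 60% US, with two unbalanced alternatives below.
- Proportional-odds treatment effect with log odds ratio 1.2.
- Age and region each have a prognostic log odds ratio of 0, 0.5, 1.0, 1.5 or 2.5, that is, odds ratios of 1, 1.65, 2.7, 4.5 and 12.

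**Formulas**
- Pooled Wilcoxon: z = (W − E)/√V. W is the midrank sum in the OV101 arm, E = n₁(N+1)/2, and V = n₁n₀/[N(N−1)] × Σ(rᵢ − r̄)².
- Van Elteren: z = Σ[(W_h − E_h)/(n_h+1)] / √Σ[V_h/(n_h+1)²], ranking within each cell h.

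There were 8,000 trials per row. The standard error is √(0.05×0.95/8000) = 0.0024 for size and √(0.8×0.2/8000) = 0.0045 for power.

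**Results, N = 90, 50/50 age, 60% US**

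| Odds ratio per factor | Size, pooled | Size, stratified | Power, pooled | Power, stratified | Gain from stratifying (points) |
|---|---|---|---|---|---|
| 1 | 0.0495 | 0.0488 | 0.8046 | 0.8000 | −0.5 |
| 1.65 | 0.0469 | 0.0482 | 0.7907 | 0.7951 | +0.4 |
| 2.7 | 0.0366 | 0.0475 | 0.7656 | 0.8026 | +3.7 |
| 4.5 | 0.0266 | 0.0495 | 0.7116 | 0.8038 | +9.2 |
| 12 | 0.0099 | 0.0503 | 0.5337 | 0.7969 | +26.3 |

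**Variations**
- N = 80: at odds ratio 1, power is 0.7564 pooled and 0.7491 stratified (−0.7 point); at 2.7, 0.7261 and 0.7645 (+3.8).
- Age 73/27 with 80% US, or age 50/50 with 90% US, N = 90: the gain falls to 2.7 and 2.4 points at 2.7, and to 6.2 and 6.5 points at 4.5.
- Exact test by full enumeration, 45 per arm, no strata effect, 3,000 trials: size 0.050, power 0.796. Exactness alone does not make the test conservative here.
- Applying the 0.5 correction to the normal approximation changed power by at most 0.4 point (largest change 0.4748 to 0.4712).

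**Limits.** Rows with prognostic strata use the tie-corrected normal approximation, not the exact test. The dropout ranking in SAP 3.8.6 was not simulated; the same mechanism applies, but no size of loss is claimed for it. Its trigger is within reach: 90 randomised against a target of 80 completing leaves a margin of 10/90 = 11%, though that is a planning margin and not a forecast.

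**The case against.** The strongest reply is that the harm is hypothetical. CGI-I-AS is already a rating of change from the child's own baseline, and nothing in the documents shows that age or region predicts it. The Phase 2 remark in Protocol Section 1, that improvement on once-daily dosing was seen irrespective of age, concerns the treatment effect and not prognosis. A reader might infer from the design that the pooled tests simply are conservative and underpowered. The first two rows of the table do not support that: with no or weak prognosis the pooled test is as good. This stands, and the point is conditional for that reason.

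It can also be said that no decision rests on these tests and that a pooled rank test is valid. Both are true. A reader might infer a threat to the primary conclusion or to type I error control; the documents give no ground for either.

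Third, adjusted analyses that do not assume normality already exist: the responder models use a logit link with both strata. They help with diagnosis, but they dichotomise the scale and so do not replace a rank test of the full score.

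Fourth, stratifying does not make the rank test fully comparable with the MMRM, because it still drops Week 6, and four cells are not the same as two additive effects. This stands. The gain in comparability is with the Week 12 ANOVA.

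Fifth, cells may be small, since region has no minimum and SAP 3.1.7 already declines centre and country adjustment because numbers are sparse. This is a reason for a pooling rule, not for dropping both factors.

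Last, the 0.5 correction might be read as an error in the analysis. SAP 3.8.1 says that the exact p-value is what will be reported, so the phrase is superfluous and need not alter the result.

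**Conclusion.** The omission is real: both rank tests name no strata although the models around them adjust for age group and region. Its consequence depends on prognosis, which the documents leave unknown. On the assumptions listed, a material loss needs fairly strong effects of both factors: about 2.4 to 3.8 points of power at an odds ratio near 2.7 each, with size about 3.7% to 4.1%, and under 1 point near 1.65. The trade nevertheless favours stratifying, which costs about 0.5 point (0.7 at N = 80) when the strata do not matter.

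The error goes in one direction only. Type I error is not raised by ignoring the strata, and the testing sequence is untouched. This is a minor improvement whose value lies in making a disagreement between the rank test and the adjusted Week 12 analysis interpretable.

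**What to change.** - In SAP 3.8.1, replace the pooled Wilcoxon with a van Elteren (stratified Wilcoxon) test by age group × region, for the FAS and PPS. State whether the p-value is asymptotic or from permutation within strata.
- In SAP 3.8.6, keep the ordering of completers and dropouts, but rank within each cell and combine in the same way.
- Prespecify a pooling rule that is applied blind to treatment: for example, stratify by age group only if any of the four cells falls below a size written into the SAP. An open-ended choice to collapse region would add discretion after the data are seen.
- Keep the Hodges–Lehmann estimate and label it descriptive and unstratified.
- Delete the continuity correction from the description of the exact test (editorial).
- Bring Protocol 7.8.1 into line, or record the change and its reason in the SAP, as Protocol 7.1 allows for changes that are not substantial.

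The cost is SAP wording, a stratified procedure call and the small power loss if the strata prove uninformative. Trial conduct, the primary analysis and alpha are unchanged.
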